11.4 Analyses

Adverse events will be categorized by organ system and severity and summarized as frequency counts and percentages. Other categorical data, such as clinical response, will be summarized similarly. Measured data, such as immune response, will be summarized as medians and ranges. All tests of statistical significance will be 2-sided and p-values will generally not be adjusted for multiple comparisons.

11.4.1 **Toxicity:** APN401 will be considered tolerable if $\leq 1/6$ or if overall $\leq 3/12$ patients (i.e. an observed toxicity rate of at most 30%) experience grade 3-4 toxicity. With this design the likelihood of stopping early and rejecting the therapy as too toxic is $\leq 11.4\%$ if the true grade 3-4 toxicity rate is $\leq 10\%$ and $> 76.7\%$ if it is $> 40\%$. The overall likelihood of declaring APN401 too toxic is $\leq 1.2\%$ and $> 62\%$, respectively in these scenarios.

11.4.2 **Immune response:** APN401 will be considered immunologically active if PBMC IFN- γ production in response to anti-CD3/28 stimulation or to one or more tumor antigens is significantly increased or if neutrophil to lymphocyte ratio is significantly decreased post-therapy (week 9) compared to pre therapy. Immune responses will be summarized as medians and ranges. The effects of treatment on these markers individually will be analyzed using paired t-tests or the non-parametric counterpart. With 12 patients there will be statistical power equal to 80% to detect 1 standard deviation change in these markers following treatment. All tests will be 2-sided and $P < 0.05$ will be considered significant.

Safety and Immunologic Activity of Multiple Infusions of APN401
Wake Forest Baptist Comprehensive Cancer Center
CCCWU 03716

11.4.3 Clinical response and survival: Clinical response will be assessed by RECIST and summarized as frequency counts and percentages. Progression-free survival and overall survival are calculated from the initial infusion to confirmation of progression or death. Exploratory survival plots will be estimated using the Kaplan Meier approach and median PFS and OS will be estimated if enough events occur.

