MAIN INCLUSION CRITERIA	
 Signed written informed consent Histologically confirmed metastatic or inoperable solid tumor no longer responding to standard therapies Must be at least 4 weeks since prior systemic therapy, radiation and/or surgery ECOG performance status 0-1 Hematocrit $\geq 28\%$, WBC $>3000/\mu\text{l}$, and platelets $>100,000/\mu\text{l}$ Creatinine $\leq 1.6 \text{ mg/dl}$ ALT and AST <2.5 fold the upper limit of normal and total bilirubin $\leq 1.6 \text{ mg/dl}$
MAIN EXCLUSION CRITERIA	
 Pregnant or breastfeeding patients Untreated, progressing, or symptomatic brain metastasis HIV, hepatitis B, or hepatitis C (active) infection Active autoimmune disease Ongoing requirement for an immunosuppressive treatment Significant cardiovascular or pulmonary disease
TREATMENT PLAN	
 PBMC for infusions will be collected by leukapheresis the day prior to infusion. Patients will be administered three infusions separated by 4 weeks Blood will be drawn pre-therapy and at 3, 5, 9, and 10 weeks, and then every 8 weeks for immune assessments Imaging will be performed pre-therapy and 2 weeks after infusion 3 and then every 8 weeks for clinical response Six patients will be treated initially. If a dose limiting toxicity (DLT) is observed in $\leq 1/6$, than an additional four patients will be enrolled to allow evaluation of laboratory correlates. Enrollment will be suspended if $>1/6$ or $>3/12$ patients manifest DLT
LABORATORY CORRELATES	
 PBMC cytokine response Circulating immunocytes
POPULATION SIZE	
 Two to 12 eligible and evaluable patients
STUDY DURATION	
 Patients will be followed for toxicity until objective disease progression or 1 year, whichever occurs first.

Safety and Immunologic Activity of Multiple Infusions of APN401
Wake Forest Baptist Comprehensive Cancer Center
CCCWU 03716

Contents

1.0	Background	6
1.1	Adoptive cellular immunotherapy	6
1.2	Cbl-b	6
1.3	APN401	7
1.4	Phase 1 study of single infusion of APN401	7
1.5	Study rationale	7
2.0	Objectives	8
2.1	Primary	8
2.2	Secondary	8
3.0	Selection of Patients	8
3.1	Inclusion criteria	8
3.2	Exclusion criteria	9
4.0	Patient Registration	10
5.0	Treatment Plan	11
5.1	Dosing	11
5.2	Leukapheresis	11
5.3	Infusion	11
5.4	Supportive care guidelines	12
5.5	Nursing implications	13
5.7	Duration of follow-up	14

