5.0 Treatment Plan

5.1 Dosing

- 5.1.1 Leukapheresis to collect PBMC for infusion will be performed the day prior to infusion. Patients will be administered three infusions of APN401 at 50×10^6 cells/kg IV, separated by 4 weeks (reference Appendix I). Leukapheresis and administration of APN401 can be delayed up to 3 weeks at the physician's discretion. Subsequent treatment must occur 28 days after prior treatment.
- 5.1.2 Six patients will be treated initially. Should >1/6 subjects experience greater than grade 3 or 4 toxicity, further enrollment of study subjects and further administration of the study agent will stop pending assessment of the risk.
- 5.1.3 If DLT is observed in $\leq 1/6$, than an additional four patients (a total of 12) will be enrolled to allow evaluation of laboratory correlates. Enrollment will be suspended if >1/6 or >3/12 patients manifest DLT

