11.3.2 Sample size

A total of up to 12 patients will be treated to allow evaluation of laboratory correlates. The design allows for an interim analysis to occur after the first 6 patients are enrolled. If 1 or less experience a grade 3-4 toxicity then 4 more will be enrolled, if 3 or less experience a grade 3-4 toxicity the agent will not be considered too toxic. With this sample size, during the first stage of the trial, if the true toxicity rate is 10% (or less) the trial will stop with 11% probability, whereas if the true toxicity rate is 40% (or higher) then the trial will stop with 76.7% probability. Likewise, if the trial continues to 12 patients, if the true toxicity rate is 10% or less the probability of observing more than 3 toxicities is 1.2% and if the true toxicity rate is 40% or more then the probability of observing more than 3 toxicities is 62%.

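### The tolerability sentence in 11.4.1 joins its two boundaries with 'or', which conflicts with 11.3.2, 5.1.3 and the synopsis, and its overall too-toxic probabilities fit no two-stage rule

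*Combined protocol and SAP*

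**What the plan says.** Four places bear on the toxicity decision.

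- **Section 11.4.1 (the verdict).** "APN401 will be considered tolerable if $\leq 1/6$ or if overall $\leq 3/12$ patients" have grade 3-4 toxicity. The section then gives the chance of stopping early and rejecting the therapy (at most 11.4% at a true rate of 10%, above 76.7% at 40%) and an overall chance of declaring it too toxic (at most 1.2% and above 62%).
- **Section 11.3.2 (the sequence).** "The design allows for an interim analysis to occur after the first 6 patients are enrolled". Then: "If 1 or less experience a grade 3-4 toxicity then 4 more will be enrolled", and "if 3 or less experience a grade 3-4 toxicity the agent will not be considered too toxic". It attaches the 1.2% and 62% to seeing more than 3 toxicities if the trial goes on to 12 patients.
- **Section 5.1.3 (enrolment).** "If DLT is observed in $\leq 1/6$, than an additional four patients (a total of 12) will be enrolled", and "Enrollment will be suspended if >1/6 or >3/12 patients manifest DLT".
- **Synopsis, treatment plan.** The same suspension rule: "Enrollment will be suspended if $>1/6$ or $>3/12$ patients manifest DLT".

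**The concern.** In 5.1.3 and the synopsis, *or* joins two adverse conditions, so either one alone is adverse. The favourable outcome is the complement of that: at most 1/6 **and** at most 3/12. Section 11.4.1 turns the inequalities round but keeps the *or*, which makes either favourable condition sufficient.

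Suppose 1 of the first 6 patients has a grade 3-4 toxicity and 3 of the next 4 do. The total is 4 of 10. The literal 11.4.1 sentence calls this tolerable because the first clause was met. Section 11.3.2 reserves its favourable finding for a total of 3 or fewer.

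Section 11.4.1 is the only place that defines tolerable, and toxicity is the primary objective. For a trial that passes stage 1 and then exceeds 3 events, two careful analysts could report opposite conclusions, each citing the plan. The overall probabilities printed beside the rule ought to show which version was meant, so they were checked as well.

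**Working it through.** **Inputs.** Stage 1 has 6 patients and passes with at most 1 event; the overall limit is 3 events; the true rates are 10% and 40% (11.3.2, 11.4.1). The second stage is 4 patients (the additional number in 11.3.2, 5.1.3 and the synopsis) or 6 (needed to reach the stated 12). Both are carried through. Let X1 be the stage-1 count and X2 the stage-2 count, independent binomials with rate p.

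**1. The plan's stage-1 figures.** P(X1≥2) = 1 − (1−p)^6 − 6p(1−p)^5.
- p = 0.10: 1 − 0.5314 − 0.3543 = 0.1143.
- p = 0.40: 1 − 0.0467 − 0.1866 = 0.7667.

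The stated 11.4% and 76.7% reproduce.

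**2. The plan's overall figures.** A single look for more than 3 events gives:
- 12 patients: P(≥4) = 2.56% and 77.5%. These are not the stated 1.2% and 62%.
- 10 patients: P(≥4) = 1.28% and 61.8%. These match, with 1.28% apparently truncated to 1.2%.

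So the overall figures are a one-look calculation on 10 patients that leaves out stage 1. If a stage-1 stop is a rejection, as 11.4.1 describes it, the overall rejection probability is the stage-1 probability plus a non-negative term. It cannot be 1.2% when stage 1 alone gives 11.4%, or 62% when stage 1 alone gives 76.7%.

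**3. Literal *or*, with a stage-1 stop.** Tolerable whenever X1≤1. At p = 0.40: 0.0467 + 0.1866 = 0.2333. The size of stage 2 makes no difference.

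**4. Both boundaries required.** The late rejection added by stage 2 is P(X1=0)·P(X2≥4) + P(X1=1)·P(X2≥3).
- p = 0.40, 4 more: 0.0467×0.0256 + 0.1866×0.1792 = 0.0346.
- p = 0.40, 6 more: 0.0467×0.1792 + 0.1866×0.4557 = 0.0934.
- p = 0.10, 4 more: 0.5314×0.0001 + 0.3543×0.0037 = 0.0014.
- p = 0.10, 6 more: 0.5314×0.0013 + 0.3543×0.0159 = 0.0063.

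| | Literal *or*, stage-1 stop | Both, 6+4 | Both, 6+6 |
|---|---|---|---|
| P(too toxic), p = 0.10 | 11.4% | 11.6% | 12.1% |
| P(too toxic), p = 0.40 | 76.7% | 80.1% | 86.0% |
| P(tolerable), p = 0.40 | 23.3% | 19.9% | 14.0% |

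**5. Trials affected.** Among trials that pass stage 1 at p = 0.40, the share that then exceeds 3 events is 0.0346/0.2333 = 14.8% (6+4) or 0.0934/0.2333 = 40.0% (6+6). The literal sentence would call all of them tolerable.

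**The case against.** The best defence is that the plan, read as a whole, shows what was meant. Section 11.3.2 is sequential: after a stage-1 pass more patients are enrolled, and the total decides. It gives a probability for more than 3 events if the trial continues, and 11.4.1 quotes an overall too-toxic probability apart from the stage-1 one. Neither would serve a purpose if at most 1/6 settled the matter. The *or* can also be read benignly: use the first limit if the trial ends at 6 patients and the second if it goes on.

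Much of this stands. A reader might infer that under this plan stage 2 can never undo a stage-1 pass. The documents do not support that; it is true only of the 11.4.1 sentence taken alone. Still, no passage says outright that more than 3 events after a stage-1 pass means not tolerable. Section 11.3.2 states only the favourable side, 5.1.3 and the synopsis govern enrolment, and the printed probabilities describe neither reading.

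A reader might also infer the converse: because 5.1.2 stops only pending a risk assessment, dosing could resume after a stage-1 failure and a final total of at most 3 would rescue the product. The documents do not set out that path. Section 11.4.1 describes the early stop as rejecting the therapy, and its 11.4% and 76.7% are exactly P(X1≥2).

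Two further limits apply. Section 5.1.3 and the synopsis count DLT (defined in 8.2), while Section 11 counts grade 3-4 toxicity, so the suspension rule is not an exact complement of the verdict rule. And the larger contrast needs six more patients, whereas the text that numbers the additional patients says four.

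**Conclusion.** The point holds as a defect of wording and of stated operating characteristics. The 11.4.1 verdict sentence, applied literally, conflicts with the sequential rule in 11.3.2 and with the direction of the boundaries in 5.1.3 and the synopsis. It does not show that the design as a whole disables stage 2.

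At a true rate of 40%, the literal wording raises the chance of declaring APN401 tolerable by 3.5 percentage points (6+4) or 9.3 points (6+6), compared with requiring both boundaries. At 10%, requiring both adds only 0.1 or 0.6 points to the too-toxic probability. Separately, the stated overall 1.2% and 62% are wrong for any rule in which a stage-1 stop is a rejection.

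These figures assume independent patients with a common event rate, one event definition at both looks, all planned patients evaluable, and a trial that ends on a stage-1 failure. The reported toxicity counts and percentages are unaffected; only the tolerability verdict and its quoted error rates change.

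**What to change.** Reconcile the verdict sentence in 11.4.1 with 11.3.2, 5.1.3 and the synopsis, so that one statement says how the two boundaries combine. The same edit must settle two things on which the calculation depends:

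- **Total sample size.** Six plus four is 10, but the documents also say 12. The gloss in 11.4.1, "i.e. an observed toxicity rate of at most 30%) experience grade 3-4 toxicity", fits 3/10 (30%) and not 3/12 (25%).
- **Counted event.** Grade 3-4 toxicity or DLT, used consistently.

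Then replace the overall too-toxic probabilities in 11.4.1, and the matching stage-2 figures in 11.3.2, with values for the rule that is kept. If both boundaries must hold, the overall values at true rates of 10% and 40% are 11.6% and 80.1% for 6+4, or 12.1% and 86.0% for 6+6. Which stopping rule is clinically appropriate is for the sponsor and investigator to decide.

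The cost is a short text amendment across these sections and a recalculation. Stating the combination rule and correcting the probabilities adds no visits or data collection; the number of patients depends only on whether 10 or 12 is confirmed.

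### Section 11.4.1 prints an overall chance of declaring APN401 too toxic (1.2% and 62%) that is below its own chance of rejecting early (11.4% and 76.7%)

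*Combined protocol and SAP*

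**What the plan says.** Six patients are treated first, and section 11.3.2 places an interim look there. The same section sets the second stage: "If 1 or less experience a grade 3-4 toxicity then 4 more will be enrolled". It accepts the agent if no more than three patients in all have a grade 3-4 toxicity. It also gives the maximum as 12, although six plus four is ten.

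Section 11.4.1 states the operating characteristics in two consecutive sentences:

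- "With this design the likelihood of stopping early and rejecting the therapy as too toxic is" at most 11.4% for a true rate of 10% or less, and above 76.7% for a true rate above 40%.
- "The overall likelihood of declaring APN401 too toxic is" at most 1.2% and above 62%, respectively, in the same scenarios.

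Section 11.3.2 uses 1.2% and 62% again, there for a trial that goes on to 12 patients: "if the true toxicity rate is 40% or more then the probability of observing more than 3 toxicities is 62" (percent).

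The treatment plan is less definite about what the first stop means. Under 5.1.2, "further enrollment of study subjects and further administration of the study agent will stop pending assessment of the risk". Under 5.1.3, "Enrollment will be suspended if >1/6 or >3/12 patients manifest DLT".

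**The concern.** A product rejected after six patients has been declared too toxic. The overall probability of that verdict therefore contains the early probability and must be at least as large. Section 11.4.1 prints the reverse.

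The two halves of the pair fail differently. With a final stop, the upper bound of 1.2% at a 10% rate is false. The lower bound of 62% at a 40% rate is literally true, but it is looser than the 76.7% printed one sentence before it.

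Toxicity is the primary outcome, and sections 11.3.2 and 11.4.1 give the only operating characteristics for the tolerability verdict. A reader who relies on the overall sentence would think that the rule discards a 10%-toxic product about once in a hundred trials and misses a 40%-toxic product in more than a third. Both impressions are wrong if the stop is final.

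**Working it through.** **Inputs.** From 11.3.2 and 11.4.1: six patients in stage 1; stop if two or more have a toxicity; four more patients otherwise; too toxic if four or more have a toxicity in total; true rates p = 0.10 and 0.40. Because the plan also says 12, a second stage of six is computed alongside. One event rate per patient is assumed to apply at both looks.

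**Stage 1, reproducing the plan.** P(stop) = 1 − (1−p)⁶ − 6p(1−p)⁵.

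- p = 0.10: 1 − 0.5314 − 0.3543 = 0.1143
- p = 0.40: 1 − 0.0467 − 0.1866 = 0.7667

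These match the printed 11.4% and 76.7%.

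**Source of the overall pair.** Single-stage P(X ≥ 4) in 10 patients is 0.0128 at p = 0.10 and 0.6177 at p = 0.40. That matches 1.2% (truncated) and 62% (rounded). None of the other calculations below matches both numbers.

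**Correct overall probability with a final stop.** Add to P(stop) the chance of passing stage 1 and then reaching four. With Y the number of toxicities in stage 2:

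addition = P(X₁=0)·P(Y≥4) + P(X₁=1)·P(Y≥3)

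- Four more, p = 0.10: 0.5314 × 0.0001 + 0.3543 × 0.0037 = 0.0014
- Four more, p = 0.40: 0.0467 × 0.0256 + 0.1866 × 0.1792 = 0.0346
- Six more, p = 0.10: 0.5314 × 0.00127 + 0.3543 × 0.01585 = 0.0063
- Six more, p = 0.40: 0.0467 × 0.1792 + 0.1866 × 0.4557 = 0.0934

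The last row below is the addition divided by 1 − P(stop), the chance of a late rejection among trials that pass stage 1.

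| Quantity | p = 0.10 | p = 0.40 |
|---|---|---|
| Printed as overall | ≤1.2% | >62% |
| Final stop, total 10 | 11.56% | 80.14% |
| Final stop, total 12 | 12.06% | 86.01% |
| Single stage, 10 patients | 1.28% | 61.77% |
| Single stage, 12 patients | 2.56% | 77.47% |
| Given a stage-1 pass, total 10 / total 12 | 0.15% / 0.71% | 14.85% / 40.04% |

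**The 12-patient sentence in 11.3.2.** With 12 patients, four or more toxicities have probability 2.56% and 77.47%, or 0.71% and 40.04% given a stage-1 pass. Neither pair is 1.2% and 62%.

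**The case against.** The strongest reply is that the first stop is a pause. Sections 5.1.2 and 5.1.3 speak of stopping until risk is assessed and of suspension. Section 8.5.2 requires a separate finding of unreasonable risk after a stopping rule is met. The synopsis range, "Two to 12 eligible and evaluable patients", does not settle it, since a suspension that is never lifted could also end the study early. This stands as a real ambiguity, but it does not rescue the text. If a pause is meant, 11.4.1 is wrong to call 11.4% and 76.7% rejection. With 12 patients, even lifting every pause gives 2.56% and 77.47%.

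A second reply takes the word *or* in 11.4.1 literally, so that the agent is too toxic only if it fails both limits. The probability is then the single-stage value minus the addition above: 1.14% and 58.3% for 10 patients, or 1.93% and 68.1% for 12. Neither pair matches, and this reading also conflicts with rejecting early.

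A third reply is that the 12 in 11.3.2 is the slip. Four more patients make ten, and the 30% ceiling in 11.4.1 is 3/10, whereas 3/12 is 25%. That is plausible. The 11.3.2 figures would then be right, apart from rounding, as an unconditional 10-patient tail, but the sentence would still need its patient number corrected and its conditioning made clear.

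It is also fair that the correct stage-1 figures stand beside the wrong ones. True overall false rejection is only 0.2 to 0.7 points above the printed 11.4%, so a careful reader may be puzzled more than misled. And no stopping count changes.

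**Conclusion.** The point holds. As labelled in 11.4.1, an overall rejection probability of at most 1.2% cannot sit beside an early-rejection probability of 11.4%. The overall pair is a 10-patient single-stage calculation that gives the stop after six no effect.

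If the stop is final, the overall chance of declaring APN401 too toxic is 11.6% to 12.1% at a 10% true rate, about ten times the printed figure (11.56/1.2 = 9.6; 12.06/1.2 = 10.1). At a 40% true rate it is 80.1% to 86.0%, which is 18 to 24 points above the printed bound. The ranges reflect the unresolved total of 10 or 12.

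Two assumptions matter. The first is that the stop is final, as the word *rejecting* in 11.4.1 implies but 5.1 does not confirm. The second is one event definition at both looks, whereas 5.1.2 refers to toxicity greater than grade 3 or 4, 5.1.3 to DLT, and 11.4.1 to grade 3-4 toxicity. The error lies in the stated properties of the rule; the stopping limits themselves are unaffected.

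**What to change.** First decide what more than one toxicity in six means, and say it the same way in 5.1.2, 5.1.3 and 11.4.1. Settle whether the total is 10 or 12. Then restate the probabilities to match:

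- **Final verdict (the reading closest to section 11).** State that the limit of three overall applies only to trials that passed stage 1. Keep 11.4% and 76.7% as early rejection. Replace the overall pair with 11.6% and 80.1% (total 10) or 12.1% and 86.0% (total 12).
- **Reversible pause.** Relabel 11.4% and 76.7% as the probability of a pause. Give 1.3% and 61.8% (total 10) or 2.6% and 77.5% (total 12) as the bounding case in which every pause is lifted.

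Correct the matching sentence in 11.3.2 and say whether it is conditional on passing stage 1. For 12 patients the figures are 2.6% and 77.5% unconditionally, or 0.7% and 40.0% given a pass. For 10 they are 1.3% and 61.8%, or 0.15% and 14.9%.

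The cost is wording and a few restated numbers, with no added patients or procedures. Under the final-verdict reading, the sponsor must accept a stated false-rejection rate of about 12% at a 10% true rate in place of 1.2%.

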E. Serum albumin, urea or BUN, creatinine, ALT, AST, LDH, alkaline phosphatase, direct and total bilirubin, glucose, total protein, sodium, potassium, chloride, CO₂, calcium, phosphorus, and uric acid. These labs should be obtained less than 36 hours prior to the treatment.

F. Women of child bearing potential must have a negative serum or urine pregnancy test (minimum sensitivity 25 IU/L or equivalent units of HCG) at screening. A pregnancy test should also be obtained at any time if there are clinical concerns for possible pregnancy.

G. Imaging should include a chest and abdomen CT. Other types of imaging and/or imaging of other sites should be obtained as clinically indicated to document extent of cancer. If restaging imaging indicates partial or complete response, repeat confirmatory imaging should be obtained in 4 weeks (but

Safety and Immunologic Activity of Multiple Infusions of APN401
Wake Forest Baptist Comprehensive Cancer Center
CCCFU 03716

no sooner than 4 weeks).

H. CA19-9 in patients with pancreatic cancer, CEA in patients with colorectal cancer, and other standard-of-care tumor markers as clinically indicated.

Repeat assessment not required if completed within 2 months of pre-study or early termination visit.

I. On Days 0, 28 and 56, the immune response testing will be taken from the leukapheresis product. On Day 15 and in the follow-up phase, collect 30 ml of blood (3 vials) into 10 ml EDTA tubes. If immune response labs have been collected within 4 weeks prior to the off study/ termination visit, re-collection is not required.

J. Peripheral blood laboratory studies performed in order to determine patient eligibility must be performed within 28 days of study entry. Radiographic and other tests performed in order to determine patient eligibility must be performed within 28 days of study entry.

K. Follow-up radiologic procedures used to assess outcome should be performed within 7 working days of the scheduled time.

L. Patients will be observed until objective disease progression or 1 year, whichever occurs first.

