M. Off study/early termination assessments are only indicated for patients who do not complete all study visits (until week 58) /Follow-Up phase. These assessments should occur no more than 4 weeks after the discontinuation of study treatment. If the subject had not undergone imaging within the past 6 weeks re-imaging is indicated. If a patient discontinues treatment for any reason other than progression, imaging will be done every 12 weeks until progression.

N. Must occur the day following leukapheresis day.

O. Following the week 18 visit only documentation of anti-cancer treatment.

P. Adverse events will be recorded on an ongoing basis and up to 2 months following the administration of the test drug.

Q. Physical Exam may be completed +/- 2 days of visit.

Safety and Immunologic Activity of Multiple Infusions of APN401
Wake Forest Baptist Comprehensive Cancer Center
WFBCCC 03716

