11.1.2 Secondary Outcome

- To determine the immunologic effects of multiple infusions of APN401 through monitoring immune response in vitro by measuring IFN production, frequency of immune cells, and neutrophil to lymphocyte ratio for one year.
- To document clinical response and survival using from RECIST criteria and progression free survival and overall survival for five years, respectively.

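### The week-9 endpoint that section 11.4.2 calls post-therapy is, by the study calendar, sampled the day before infusion 3, and the documents disagree on immune sampling two weeks after that infusion

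*Combined protocol and SAP*

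**What the plan says.** **Decision rule.** Section 11.4.2 compares pre-therapy with one later time point. Activity is declared if IFN-gamma production rises after anti-CD3/28 or antigen stimulation, or if the neutrophil to lymphocyte ratio falls. The rule ends: "tumor antigens is significantly increased or if neutrophil to lymphocyte ratio is significantly decreased post-therapy (week 9) compared to pre therapy".

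**Infusions.** Three are planned, on Days 1, 29 and 57 of the Study Calendar (section 6.0). Section 5.1.1 states: "Leukapheresis to collect PBMC for infusion will be performed the day prior to infusion". Calendar footnote N, attached to Days 29 and 57, repeats the order: "Must occur the day following leukapheresis day". Section 5.1.1 also says: "Leukapheresis and administration of APN401 can be delayed up to 3 weeks".

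**Week-9 sample.** The calendar marks immune response on Day 56, not Day 57. Footnote I gives the source: "On Days 0, 28 and 56, the immune response testing will be taken from the leukapheresis product". The CBC with differential is likewise marked on Day 56 and not Day 57.

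**Other sampling text.**
- Synopsis, treatment plan: "Blood will be drawn pre-therapy and at 3, 5, 9, and 10 weeks, and then every 8 weeks for immune assessments".
- Calendar footnote I: "On Day 15 and in the follow-up phase, collect 30 ml of blood (3 vials) into 10 ml EDTA tubes".
- Section 10.1: 20 ml of peripheral blood at baseline, on Days 29 and 57, and at eight-week intervals after that.
- Section 11.1.2 describes the secondary outcome as "monitoring immune response in vitro by measuring IFN production, frequency of immune cells, and neutrophil to lymphocyte ratio for one year".

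**The concern.** A reader will take a post-therapy result to describe the full three-infusion course. If the sample precedes infusion 3, a positive or negative finding under 11.4.2 describes two infusions and says nothing direct about the third. Section 1.5 names immunologic activity, together with safety, as the evidence for moving to phase II, and 11.4.2 is the only place that defines it.

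The second issue is whether data after infusion 3 will exist soon enough to help. Staff who follow the synopsis will draw immune blood two weeks after infusion 3. Staff who follow section 10.1, or the calendar row as extracted, will not, and a missed IFN-gamma or flow cytometry sample cannot be recovered. The neutrophil to lymphocyte ratio is less exposed, because a CBC differential is scheduled on Day 71 in any case.

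**Working it through.** The check is day arithmetic on the calendar. The power statement in 11.4.2 is not needed for it.

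**1. Week labels.** With Day 0 in week 1, day d falls in week floor(d/7) + 1.
- Day 15: floor(2.1) + 1 = week 3, as labelled.
- Day 28: 4 + 1 = week 5, as labelled.
- Day 56: 8 + 1 = week 9, as labelled.
- Day 71: floor(10.1) + 1 = week 11, although the calendar labels it week 10.

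The synopsis's week 10 is matched to Day 71 through the calendar's own label.

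**2. The week-9 sample against the infusions.**
- To infusion 3: 57 − 56 = 1 day before.
- From infusion 2: 56 − 29 = 27 days after, on schedule.
- Infusions already given: 2 of 3.

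Visit windows and permitted delays do not change the order. The sample is the leukapheresis product itself, and the infusion follows one day after leukapheresis, so the two move together. A delay does change the interval: 27 days could become 27 + 21 = 48.

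**3. Immune sampling by source.**

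| Source | Before infusion 1 | Day 15 | Day 28/29 | Day 56/57 | Day 71 | Next |
|---|---|---|---|---|---|---|
| Synopsis | yes | week 3 | week 5 | week 9 | week 10 | every 8 weeks |
| Calendar row, as extracted | Day 0 | yes | Day 28 | Day 56 | blank | week 18 |
| Footnote I | Day 0, leukapheresis product | blood, 30 ml | Day 28, leukapheresis product | Day 56, leukapheresis product | blood, 30 ml, if Day 71 is in the follow-up phase | blood, 30 ml |
| Section 10.1 | blood, 20 ml | none | Day 29, blood | Day 57, blood | none | 8 weeks later |

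**4. First immune sample clearly after infusion 3 (Day 57).**
- Synopsis: 71 − 57 = 14 days; 11 to 17 with the ±3-day window and infusion 3 on Day 57.
- Section 10.1: 57 + 56 = Day 113, so 56 days, or 8 weeks.
- Calendar row, by day count: week 18 is Days 119 to 125. Subtracting 57 gives 62 to 68 days, or 55 to 75 with the ±1-week window.
- Calendar row, counted as 8 weeks from Day 71: 71 + 56 = Day 127, and 127 − 57 = 70 days, or 63 to 77 with the window.

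**5. Early-termination visit.** The calendar marks an immune sample there, and footnote M places the visit within 4 weeks of stopping treatment. Footnote I waives re-collection if a sample was taken in the previous 4 weeks. On schedule, the Day 56 sample would allow that waiver up to 56 + 28 = Day 84.

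**6. Why Day 71 needs an anchor.** If infusion 3 is delayed by 3 weeks it falls on Day 57 + 21 = 78. A draw fixed at Day 71 from the start of treatment would then be 7 days before infusion 3.

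**The case against.** **The time point is not hidden.** Section 11.4.2 states week 9 openly, and comparing Day 56 with Day 0 pairs leukapheresis product with leukapheresis product while keeping patients who leave later. This stands. The week-9 comparison is a sound on-treatment comparison, and only its label is wrong.

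**Section 10.1 might rescue the label.** Day 57 is also in week 9, and a draw after the infusion that day is not excluded. A reader might therefore infer too much from a statement that the rule can only ever show two infusions; the text does not support anything that absolute. But 10.1 does not say before or after, it conflicts with footnote I on day and matrix, and at best the sample is hours after infusion 3.

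**The Day 71 gap rests partly on a blank cell in an extracted table.** This is also fair. Footnote I supports the synopsis if Day 71 belongs to the follow-up phase, as the extracted header suggests. The conflict between the synopsis and section 10.1 is in plain text and does not depend on the table.

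**Three further inferences go beyond the documents.** Two infusions do not fail objective 2.2.1, because two are still multiple. Data after infusion 3 are not absent, since 11.1.2 plans immune monitoring for a year; they simply do not enter the 11.4.2 rule. And no passage makes 11.4.2 the sole criterion for phase II.

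**Conclusion.** The concern holds as a wrong label and a sampling conflict. By the calendar, the 11.4.2 rule is evaluated one day before infusion 3, after two of three infusions. This applies to IFN-gamma through footnote I. It applies to the neutrophil to lymphocyte ratio if its source is the calendar's CBC differential, which the documents do not state.

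The documents also disagree on whether immune blood is drawn at Day 71. If it is not, the first scheduled immune sample clearly after infusion 3 moves from about 2 weeks to about 8 weeks (10.1) or 9 to 10 weeks (calendar), apart from early-termination samples. These intervals assume on-schedule infusions and that the calendar row was extracted correctly.

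A reader might infer that the decision must move to Day 71. The documents do not require that. It would lose patients who leave between Days 56 and 71. It would need a peripheral-blood baseline, and 10.1 does not say where its baseline falls relative to the Day 0 leukapheresis. Day 71 is also 14 days after the last infusion against 27 for Day 56, so a difference between the two could not be credited to infusion 3 alone. It is an option for the sponsor.

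**What to change.** 1. In 11.4.2, relabel the endpoint as after two infusions and before infusion 3, defined as Day 56 versus Day 0, both from leukapheresis product for IFN-gamma. Limit the activity conclusion to that.
2. Name the source of the neutrophil to lymphocyte ratio and its timing relative to leukapheresis. Section 7.3 reports transient lymphopenia attributed to that procedure, and the calendar does not say whether the Day 0 and Day 56 counts precede it.
3. Reconcile the synopsis, calendar row, footnote I and section 10.1 on days, matrix (peripheral blood or leukapheresis product) and volume (20 or 30 ml), so that the week-10 (Day 71) draw in the synopsis is collected. Time it from the actual infusion 3 date.
4. Report the Day 71 values as the result after three infusions. Do not read Day 71 peripheral-blood IFN-gamma as a change from the Day 0 leukapheresis product; if a change is wanted, state when the peripheral-blood baseline in 10.1 is drawn.

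The cost is text edits plus one draw of 20 to 30 ml that the synopsis already lists. Items 1 and 2 need no additional sample if the existing counts are used.
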